13.2 DETERMINATION OF SAMPLE SIZE SUBJECTS

Given the previous reports, one would anticipate in this observational study that approximately 30+ % of patients would experience a significant (25%) improvement in indices of upper limb and walking mobility. Using a crossover design and treating the observations as paired within individuals, and allowing for loss to follow up during the trial, a sample size of 80 (40 in each arm) will be used.

13.3 ANALYSIS SETS

The primary analysis will be an intention to treat analysis. A secondary per protocol analysis will be carried out should this differ.

13.4 DEMOGRAPHIC AND BASELINE DISEASE CHARACTERISTICS

Demographic and baseline disease characteristic data will be summarized for each treatment group by presenting frequency distributions and descriptive statistics.

13.5 EFFICACY ANALYSIS

Primary efficacy endpoint:

An upper limb responder to fampridine will be defined as a patient with both of the two "on treatment" 9-HPT assessments (assessments 4 & 5 or 7 & 8) improving 20% from the average of the baseline assessments (1, 2 & 3).

Secondary efficacy endpoints:

- a) A secondary measure of upper limb responsiveness will be defined as a 20% improvement in from baseline in the average time taken to complete all seven tasks on the JTT “on treatment” (assessments 4 & 5 or 7 & 8) compared with baseline assessments (assessments 1,2 & 3).
- b) A mobility responder to dalfampridine will be defined as a patient with both of the two “on treatment” T25FW assessments (assessments 4 & 5 or 7 & 8) being better than the maximum of any of the four “off treatment” assessments (assessments 1, 2, 3, & 9). Otherwise the patient will be deemed a non-responder.
- c) The responders to the 9-HPT and/or JTT will be compared to the non-responders in relation to their changes in the DASH and AMSQ on treatment and off treatment at the baseline assessment. The change in the DASH and AMSQ in responders at Assessment 5 or 8 (week 10 or 20) will be compared to non-responders at that time-point.

Upper limb response will be examined at the end of treatment phase 1 and repeated at the end of the trial by comparing patients receiving active drug with those receiving placebo to assess any placebo effect and allow assessment of any residual beneficial effect on those who receive fampridine in treatment phase 1 and then switch to placebo in treatment phase 2. Response will again be considered as a 20% improvement in the 9HPT in the active treatment group compared with placebo and a 20% improvement from baseline in the time taken to complete all seven tasks in the JTT. See earlier comment

- d) The responders to the T25FW will be compared to the non-responders in relation to their changes in the MSWS-12 on treatment and off treatment at the baseline assessment. The change in the MSWS-12 in responders at Assessment 5 or 8 (week 10 or 20) will be compared to non-responders at that time-point.

The patients’ scores on the MSIS-29 (physical) and SF-36 will be examined in relation to the objective changes (responder/non-responder) in the 9-HPT, JTT and the T25FW.

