5.0 DOCUMENT HISTORY

Document	Date of Issue	Summary of Change
Protocol Version 2.1	03.02.2013	1. Defined walking speed removed from inclusion criteria 2. Additional questionnaire on upper limb function added (AMSQ).
Protocol Version 2.0	28.03.2012	Formatted IMB specification
Original Protocol	02.01.2012	Not applicable

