7.0 ABBREVIATIONS

AE	Adverse event
AR	Adverse reaction
CA	Competent authority
CI	Chief investigator/Co-ordinating investigator
CRF	Case report form
CRO	Contract research organisation
CT	Clinical trial
CTA	Clinical trial authorization
DASH	Disabilities arm, shoulder, hand questionnaire
ECG	Electrocardiogram
EDSS	Expanded Disability Status Scale
EU	European Union
e-CRF	Electronic case report form
GCP	Good Clinical Practice
GP	General Practitioner
9-HPT	Hole Peg test
IB	Investigators brochure
ICF	Informed consent form
ICH	International Conference on Harmonisation
IEC	Independent Ethics Committee
IMB	Irish Medicines Board
IMP	Investigational medicinal products
IMPD	Investigational medicinal product dossier
HSE	Health Service Executive
JTT	Jebson Taylor Hand Function Test
MS	Multiple Sclerosis
MSIS-29	Multiple Sclerosis Impact Scale 29
MSWS-12	Multiple Sclerosis Walking Scale
OCT-2	Organic Cation Transporter 2
PI	Principal investigator
PIL	Patient/subject information leaflet
PPMS	Primary Progressive MS
REC	Research ethics committee
ROI	Republic of Ireland
SAE	Serious adverse event
SAR	Serious adverse reaction
SmPC	Summary of product characteristics
SOP	Standard operating procedure
SPMS	Secondary Progressive MS
SVUH	St. Vincent's University Hospital, [name]
SUSAR	Suspected unexpected serious adverse reaction
T25FW	Twenty-five foot timed walk

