8.2 RATIONALE FOR THE STUDY

Treatment with fampridine (4-aminopyridine), a potassium channel blocker,^{1,2} has been shown to cause significant improvement in walking speed in one third of MS patients with motor disability.³⁻⁵ In those patients who respond, approximately a 25% improvement in walking speed was obtained with a self-reported 7 point improvement in the Multiple Sclerosis Walking Scale (MSWS-12), a patient-rated measure of walking quality and ability,^{6,7} in comparison to non-responding patients and placebo control subjects.

Pharmacologically, the K⁺ channel blocking properties of fampridine and its effects on action potential conduction in demyelinated nerve fiber preparations have been extensively characterized. At low concentrations that are relevant to clinical experience (in the range of 0.2 to 2 µM [18 to 180 ng/mL]), fampridine is able to block certain voltage-dependent K⁺ channels in neurons. It is this characteristic that appears to explain the ability of the drug to restore conduction of action potentials in some critically demyelinated nerve fibers. At higher (millimolar) concentrations, fampridine affects other types of K⁺ channels in both neural and non-neural tissues. Blockade of repolarising K⁺ currents may increase synaptic transmission throughout the nervous system by increasing the duration of the presynaptic action potential. A range of neurological effects consistent with increased excitability of nerve cells occurs with clinically relevant doses of fampridine.

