with spinal cord injury, may be broadly categorized as excitatory effects in the nervous system consistent with the K⁺ channel blocking activity of the compound in the nervous system. These AEs include dizziness, paresthesias, insomnia, balance disorders, anxiety, confusion, and seizure. In studies in MS patients, the following most frequent treatment-related AEs were also observed: urinary tract infection, asthenia, back pain, constipation, dyspepsia, and pharyngolaryngeal pain. At higher dose levels, more severe central nervous system AEs such as confusion and seizure have been seen. With the adoption of the 10 mg BID dose in extension studies, the rate of first seizure has been approximately 0.32 per 100 subject-years. This rate does not exceed the expected incidence of seizures in the MS population, particularly in the more advanced disease state with significant ambulatory disability¹⁸. However, patients were excluded from these studies if they had a history of seizure or evidence of epileptiform activity on a screening electroencephalogram. Seizures have been seen in the post marketing setting in the US although confounding factors such as seizure history and use of concomitant medications that have been associated with a seizure risk may have contributed to the occurrence of seizures in some patients. No new safety signal has been detected as of March 2011.

The FDA has recently approved Fampridine, a slow release preparation, for use in the MS patient population.⁸ It has also recently been approved in Europe (20th July 2011).¹⁷ Most studies of fampridine assessed timed walking over twenty-five feet and the Multiple Sclerosis Walking Scale-12 (MSWS-12).³⁻⁵ Deficits in arm and hand function are commonly found in patients with SPMS and PPMS and can have an impact in performing many activities of daily living. We propose to examine the efficacy of fampridine in upper limb function and in overall disease impact in a single centre, double blind, randomized, placebo-controlled, crossover study of patients attending St Vincent's University Hospital with significant walking and upper limb disability due to SPMS and PPMS.

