9.2 SECONDARY OBJECTIVE

Secondary objectives are:

To assess the effect of treatment with fampridine on walking mobility assessed by the Timed 25 foot Walk (T25FW) and the Multiple Sclerosis Walking Scale (MSWS-12)^{6,7}

To determine whether response or non-response to fampridine by the T25FW can be easily determined using self reported changes in the MSWS-12 alone within 4 weeks in the course of active therapy

To determine whether response or non-response to fampridine by the 9HPT or JTT can be easily determined using self reported changes in the DASH and AMSQ alone within 4 weeks on the course of active therapy

To determine whether any relation exists between improvement / lack of improvement on the T25FW and improvement/ lack of improvement on the 9-HPT or JTT.

To examine the safety of fampridine in this patient population

To assess the impact of fampridine on health related quality of life in patients with multiple sclerosis (HRQOL) as measured by the SF-36 questionnaire.

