10.3 STUDY ASSESSMENTS AND PROCEDURES

Patients likely to fulfill the inclusion criteria and not meet any exclusion criteria will be provided with information on the study and invited to attend a subsequent screening visit. Only patients who have signed the informed consent form will participate in any study related procedures including blood testing and ECG.

At screening visit (Assessment 1) subjects will have a physical examination and an EDSS score rated. Blood samples will be taken for renal and liver function and a baseline ECG performed. Patients will complete a nine-hole peg test and a JTT. T25FW will be recorded and the patients invited to complete the MSIS-29, MSWS-12, DASH, AMSQ and SF-36 questionnaires. Patients with any abnormalities on ECG, blood tests will not be invited to a baseline visit and considered a screening failure.

Following screening visit subjects fulfilling the inclusion / exclusion criteria will have two baseline visits (Assessments 2 and 3) at the end of week one and end of week two. The 9-HPT, JTT and T25FW will be repeated to allow for training effects. Patients will be randomised to group A or group B and receive study medication or placebo at baseline visit based on their blinded randomisation (Assessment 3).

The first treatment period will be from the start of week 3 until the end of week 10. Patients will have an assessment at the end of week 6 (Assessment 4) and the end of week 10 (Assessment 5). At both assessments patients will have the 9-HPT, JTT, T25FW, MSIs-29, MSWS-12, DASH, AMSQ and SF-36 recorded. Weeks 11 and 12 will be a washout period (no drug/placebo). Assessment 6 will occur at the end of week 12 and will include recording of 9-HPT, JTT, T25FW, MSIs-29, MSWS-12, DASH, AMSQ and SF-36. Any adverse events will be recorded at each visit as will the use of concomitant medications.

The second treatment period will begin at the start of week thirteen with groups A and B switching study drug / placebo in a blinded manner. The second treatment period will continue for a further 8 weeks with two more assessments at week 16 (Assessment 7) and week 20 (Assessment 8). At both of these assessments subjects will complete the 9-HPT, JTT, T25FW, MSIs-29, MSWS-12, DASH, AMSQ and SF-36. At the end of week 20 and EDSS score will be recorded. Any adverse events will be recorded at each visit as will the use of concomitant medications.

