There will be a final washout period (weeks 21 and 22) after which a final visit (assessment 9) will occur and subjects once again completing 9-HPT, JTT, T25FW, MSIs-29, MSWS-12, DASH, AMSQ and SF-36 and having an EDSS score recorded. Once again adverse events will be recorded.

(See Schedule of Events, page 15)

Figure 2: Schedule of events

Assessment	1 Screening Visit	2 Baseline Visit	3 Base - line Visit	4 Rx Phase 1	5 End of Rx Phase 1	6 End Wash- out phase	7 Rx Phase 2	8 End of Rx Phase 2	9 End of 2 week washout
Time (start/end week)	week 1 (start)	week 1 (end)	week 2 (end)	week 6 (end)	week 10 (end)	week 12 (end)	week 16 (end)	week 20 (end)	week 22 (end of trial)
Informed consent	X								
Serum pregnancy test (female subjects)	X								
EDSS	x							X	X
ECG	X								
Receiving Medication	No	No	Start drug	Continu e drug	Stop drug	Start drug	Continu e drug	Stop drug	Wash out
9- HPT	x	x	x	x	x	x	x	x	X
JTT	x	x	x	x	x	x	x	x	X
T25FW	x	x	x	x	x	x	x	x	X
MSIS-29	x		x	x	x	x	x	x	X
MSWS-12	x		x	x	x	x	x	x	X
DASH	x		x	x	x	x	x	x	X
AMSQ	x		x	x	x	x	x	x	x
SF-36	X		X	X	X	X	X	X	X
Adverse event recording				X	X	X	X	X	X
Concomitant medication recording	X		X	X	X	X	X	X	X
Study Drugs dispensed			X			X			

Description of Study Assessments

Medical and Surgical History will be recorded with particular attention on the diagnosis of MS, duration of MS and MS subtype.

Demographics

The date of birth, gender and race will be recorded.

Physical Examination

The complete physical examination will include the evaluation of the neurological system and a recording of the EDSS score and T25FW.

ECG Test

One ECG including a 12-lead examination will be performed at Screening (assessment 1).

Abnormal findings will be noted for clinical significance. The report will be signed by the investigator.

Clinical Laboratory Tests

1. Haematology: haemoglobin, WBC, RBC, platelet count
2. Biochemistry: creatinine or creatinine-clearance, sodium, potassium, liver function tests
3. All laboratory results will be reviewed and the reports signed by the investigator who will record in the CRF whether they are normal, abnormal but not clinically significant, or abnormal and clinically significant.

Pregnancy Tests

Serum pregnancy test and urine pregnancy test in women of childbearing potential will be performed.

Concomitant Medication

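### The T25FW mobility-responder rule does not say whether the maximum is a time or a speed, so the hurdle can be the slowest or the fastest off-treatment walk

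*Combined protocol and SAP*

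**What the plan says.** Secondary endpoint b) in section 13.5 requires both T25FW assessments of a treatment period (4 and 5, or 7 and 8) to satisfy "being better than the maximum of any of the four" off-treatment assessments, which are 1, 2, 3 and 9. Any other patient is a non-responder. Sections 9.4 and 10.3.2 use the same phrase for the hurdle.

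On the scale of measurement:

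- Section 7.0 expands T25FW as "Twenty-five foot timed walk".
- Section 8.2 says that most earlier studies "assessed timed walking over twenty-five feet".
- Section 10.3 asks only for "a recording of the EDSS score and T25FW" at the physical examination and lists the test at every visit, without a unit.
- Section 8.2 also describes earlier responders in terms of speed: "approximately a 25% improvement in walking speed was obtained".

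No section converts the recorded walk to a speed or says which walk the maximum is.

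**The concern.** For a time, lower is better and the numerical maximum is the worst walk. For a speed, higher is better and the maximum is the best walk. The same phrase therefore gives either a lenient hurdle (beat your slowest of four) or a strict one (beat your fastest of four). An analyst who takes the maximum of a column of recorded times gets the lenient one.

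Mobility-responder status is more than a reported proportion. It forms the groups for the MSWS-12 comparison (13.5 d), for the T25FW-based MSIS-29 and SF-36 comparisons, and for the relation between walking and upper-limb response (9.2). It is also the reference for the 9.2 objective of finding out whether MSWS-12 alone can identify response within 4 weeks. If many patients with no drug effect count as responders, those contrasts are diluted. An undefined direction also leaves the choice open until after the data are seen.

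**Working it through.** **Plan's own figure.** The documents give no null or placebo rate for this rule, so there is none to reproduce. Section 13.2 gives the sample size (80) and an anticipated improvement in 30% or more of patients.

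**Inputs from the rule.** Four off-treatment walks, two on-treatment walks, both of which must clear the hurdle.

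**Exact null rates.** Assume no drug effect, six exchangeable walks and no ties. The two on-treatment walks can occupy C(6,2) = 15 equally likely pairs of ranks.

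- Slowest-walk hurdle: met whenever the slowest of all six is an off-treatment walk. This holds in 10 of 15 placements, 4/6 = 66.7%; 80 × 2/3 = 53.3 patients.
- Fastest-walk hurdle: met only when the two on-treatment walks are the two fastest. This holds in 1 of 15 placements, 6.7%; 80/15 = 5.3 patients.

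**Departures from exchangeability.** Section 10.3 itself expects a learning effect: "The 9-HPT, JTT and T25FW will be repeated to allow for training effects". The null rates were therefore simulated with 400,000 patients per cell, mean 10 s, ties counted as non-response, visits at the scheduled weeks, three error models (lognormal, normal proportional, normal additive) and both treatment periods. These departures were assumed one at a time:

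- training effect of 5% or 10% at visits 1 and 2 (full at both, or halved at visit 2), or 10% at visit 1 only;
- 5–10% worsening or improvement over 22 weeks;
- serial correlation of 0.5–0.8 per 2 weeks;
- rounding to 0.1, 0.5 or 1 s.

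The documents give no visit-to-visit CV, so the CVs are assumptions too.

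| Visit CV | Slowest-walk hurdle | Fastest-walk hurdle |
|---|---|---|
| 5% | 37–96% | 0.2–18% |
| 10% | 49–86% (39–69 of 80) | 2–14% (1–11 of 80) |
| 15% | 55–81% | 3–13% |

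In every one of these scenarios the slowest-walk rate is at least 35 percentage points higher. A full 10% training effect at both visits 1 and 2, with CV 10%, gives 84–85% against 12–13%.

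**Sensitivity to a true effect** (same CVs and error models, no drift or training effect):

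| True time reduction | Fastest-walk hurdle, CV 5% / 10% / 15% | Slowest-walk hurdle, over all three CVs |
|---|---|---|
| 20% | 98–99% / 65–73% / 41–47% | 95–100% |
| 10% | 65–69% / 30–32% / 20–21% | 85–99% |

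**What this does to the groups.** As an illustration, assume that 30% of 80 (24 patients) have a true 20% reduction, the other 56 have none, and the CV is 10%.

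- Slowest-walk: 56 × 2/3 = 37.3 false responders and 24 × 0.95 to 24 × 1.00 = 22.8 to 24 true ones. True responders make up 22.8/60.1 to 24/61.3 = 38–39% of the group.
- Fastest-walk: 56/15 = 3.7 false responders and 24 × 0.65 to 24 × 0.73 = 15.6 to 17.5 true ones. True responders make up 15.6/19.3 to 17.5/21.3 = 81–82% of the group.

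**The case against.** The strongest reply is that only one reading is sensible. The phrase is performance language. A rule that demands both visits, uses four reference walks and defaults to non-response is built to be strict, and beating only one's worst walk would be an odd test of response. Section 8.2 speaks of speed, for which the maximum is the fastest walk. This stands as evidence of intent. Other hints are weaker: the document history mentions a removed walking-speed criterion, and the 30% in section 13.2 refers to a 25% improvement, which is a different threshold. None of these is a definition. The measure is named as a time, and the phrase read literally on times gives the lenient hurdle. All three sections use it, so none corrects another.

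A second reply concerns size.

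- The rates apply to one treatment period. If qualifying in either period counted, the null rates would be 5/6 = 83.3% and 2/15 − 1/70 = 5/42 = 11.9%. The rule defines a responder to fampridine, which points to the single active period, so the one-period rates are the relevant ones.
- The 35-point gap is not a general floor. Combining 1 s rounding, 10% worsening and serial correlation 0.8 in the second period at CV 5% brings the rates to about 17% and 0.5%. The direction is unchanged.

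A third reply is that the reach is limited, and that is correct. The primary 9-HPT endpoint, the JTT endpoint and the DASH/AMSQ comparison do not use the rule. Applied alike to both treatments, it does not by itself bias a fampridine–placebo comparison. The T25FW is recorded at all nine visits, so status can be recomputed under either reading.

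**Conclusion.** The concern holds. The hurdle is undefined in all three places where it appears, and its literal application to recorded times gives the opposite of the probable intent. Under exchangeability, no ties and no drug effect, the choice of reading moves the responder rate between 66.7% and 6.7%. Those two figures need no CV. The ranges around them rest on assumed CVs, training effects, drift, correlation and rounding, and the illustration of group make-up also assumes the responder share and effect size. That the fastest walk was intended is an inference. The defect is confined to a secondary endpoint and the analyses grouped by it. It should be fixed, but it does not threaten the primary result.

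**What to change.** Before unblinding, change only the hurdle wording in sections 9.4, 10.3.2 and 13.5, so that a mobility responder is a patient whose T25FW times at both on-treatment assessments (4 and 5, or 7 and 8) are shorter than the shortest (fastest) of the four off-treatment times (1, 2, 3 and 9). Everyone else remains a non-responder. If the sponsor meant the other hurdle, the direction still has to be stated before unblinding.

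The cost is three small edits and no new data or visits. Fewer patients will be classed as responders than under the slowest-walk reading, and the strict rule misses more true improvement when walks are variable: at CV 15% it detects 41–47% of patients with a true 20% reduction. The slowest-walk reading detects more, but at a null rate of about 67%.

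### The T25FW mobility-responder rule counts four off-treatment walks where the schedule has five; leaving out Assessment 6 sets a harder bar for sequence B than for A if any fampridine effect persists at two weeks

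*Combined protocol and SAP*

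**What the plan says.** Section 13.5 (b) defines a mobility responder by "both of the two “on treatment” T25FW assessments (assessments 4 & 5 or 7 & 8"), each "being better than the maximum of any of the four “off treatment” assessments (assessments 1, 2, 3, & 9"). The rule closes with that list of visits and classes everyone else as a non-responder: "assessments (assessments 1, 2, 3, & 9). Otherwise the patient will be deemed a non-responder". Sections 9.4 and 10.3.2 repeat the rule with the same count and the same list of visits.

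Section 10.3 describes the interval between the two treatment periods: "Weeks 11 and 12 will be a washout period (no drug/placebo). Assessment 6 will occur at the end of week 12". The T25FW is among the tests recorded there: "Assessment 6 will occur at the end of week 12 and will include recording of 9-HPT, JTT, T25FW". Dosing resumes only afterwards: "The second treatment period will begin at the start of week thirteen". Assessment 9 has the same form: "There will be a final washout period (weeks 21 and 22) after which a final visit (assessment 9) will occur".

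Section 10.3.3 defines sequence A as fampridine then placebo, and sequence B as placebo then fampridine.

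**The concern.** Assessment 6 is off treatment on the same footing as Assessment 9: each follows a two-week washout. It is also on the same footing as Assessment 3, since the schedule of events (Figure 2) marks both 3 and 6 as visits where drug is started, and the rule counts 3 as off treatment. The plan gives no reason for leaving 6 out.

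The omission matters because the two washout visits swap roles between sequences:

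| | Assessment 6 follows | Assessment 9 follows |
|---|---|---|
| Sequence A | fampridine | placebo |
| Sequence B | placebo | fampridine |

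With only Assessment 9 in the bar, a B patient must beat a walk taken two weeks after fampridine. An A patient never has to. The protocol itself allows for a residual benefit after fampridine, though it says so for upper limb response and gives no size. Worry about carryover cannot explain the omission, because B's post-fampridine walk is kept.

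T25FW responder status feeds the mobility endpoint, the MSWS-12 comparison, the MSIS-29 and SF-36 comparisons, and the objective in 9.2 that relates walking response to arm response. Any sequence-dependent misclassification passes into all of these.

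**Working it through.** **Count.** The plan states four off-treatment walks: 1, 2, 3, 9. Section 10.3 and Figure 2 give T25FW recordings with no study treatment in the preceding interval at 1, 2, 3, 6 and 9, which is five. The stated count is not reproduced.

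**Chance rate with no drug effect, trend or carryover.** All visits are then exchangeable. With k off-treatment walks, the probability that both on-treatment walks beat the fastest off-treatment walk is 2!·k!/(k+2)!.
- k = 4: 2·24/720 = 1/15 = 6.7%.
- k = 5: 2·120/5040 = 1/21 = 4.8%.
- Among 80 patients: 80/15 = 5.3 against 80/21 = 3.8, a difference of about 1.5. The rate is the same in A and B.

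**What the word maximum does.** For a timed test, maximum may mean the highest speed or the longest time. If it means the longest time, a patient passes whenever the slowest of all k+2 walks is an off-treatment one. The probability is k/(k+2): 4/6 = 66.7% with four walks and 5/7 = 71.4% with five. On that reading, adding Assessment 6 makes the rule easier.

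**Carryover.** The documents give no effect size, residual or visit-to-visit variance, so the values here are assumptions. Visits are independent and normal with within-patient SD 1 on a scale where higher is faster. Let δ be the drug effect at the two active visits and ρ the residual at the post-fampridine washout visit. The response probability is ∫[1 − Φ(m − δ)]² dF(m), where F is the distribution of the best off-treatment walk:
- Four walks, sequence A: F(m) = Φ(m)⁴.
- Four walks, sequence B: F(m) = Φ(m)³·Φ(m − ρ).
- Five walks, either sequence: F(m) = Φ(m)⁴·Φ(m − ρ).

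With five walks F is identical in A and B, so the carryover gap vanishes exactly. Simulation with 400,000 patients per sequence gives these response percentages:

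| δ | ρ | A, four | B, four | A, five | B, five |
|---|---|---|---|---|---|
| 2 | 0 | 65 | 65 | 61 | 61 |
| 2 | 0.5 | 65 | 60 | 56 | 56 |
| 1.5 | 0 | 47 | 47 | 42 | 42 |
| 1.5 | 0.75 | 47 | 38 | 35 | 35 |
| 1.5 | 1.5 | 47 | 25 | 23 | 23 |

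**Trend.** Section 10.3 mentions training effects without sizing them.
- Assumed practice gain of 0.5 SD per natural log of test number, no drug effect: A 9.1% and B 13.9% with four walks; 5.8% and 9.4% with five.
- Assumed 1 SD linear decline over 22 weeks, 2 SD effect: A 59.1% and B 42.5% with four (gap 16.6 points); 56.5% and 39.7% with five (gap 16.8 points).

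Adding Assessment 6 does not cure the trend gap. It arises because A's active visits fall at weeks 6 and 10 and B's at weeks 16 and 20.

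**The case against.** A reader might infer that the bar always differs between the sequences. The documents do not support that. The listed visits are the same for A and B, and without carryover or trend the response rates are equal whether four or five walks are used. The asymmetry is conditional on a residual effect that the documents raise only for upper limb response and do not size.

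A reader might also infer that the rule is too easy to pass by chance. On the fastest-walk reading the omission adds only 1.9 points (6.7% − 4.8%). The documents set no acceptable chance rate, and the 0.05 in section 13.7 governs tests, not the classification of single patients. The same rule could also be applied to the placebo visits as a control.

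The strongest argument against adding Assessment 6 combines the assumed practice curve with a 2 SD effect and a 0.5 SD residual. The rule as written then gives A 69.4% and B 68.5%; with Assessment 6 it gives 57.0% and 64.2%, so the change appears to create an imbalance. But practice favours B and carryover penalises B, and under these particular values the two nearly cancel. That is coincidence, not a merit of the four-walk rule. It does stand as evidence that the change addresses carryover only.

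Another route is to drop Assessment 9 and use only visits 1 to 3, as the primary 9-HPT rule does. That also removes the carryover asymmetry. It discards both post-treatment walks, however, and raises the chance rate to 2!·3!/5! = 1/10 = 10%.

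Finally, the extra walk costs real responders: in the 2 SD, 0.5 SD case A falls from 65% to 56%. That stands and is counted under the fix.

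**Conclusion.** The mismatch is certain: the schedule has five off-treatment walks, the rule names four, and no reason is given for the difference. Its consequence is conditional. If fampridine has a residual effect on walking at two weeks, B faces a harder bar than A. Under the assumed values the gap is 5 points (65% against 60%) with a 2 SD effect and 0.5 SD residual, 9 points (47% against 38%) with 1.5 and 0.75 SD, and 22 points (47% against 25%) with 1.5 and 1.5 SD. In each case it closes once Assessment 6 is included. These figures rest on independent normal visits, no trend and the fastest-walk reading.

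The wording of the bar needs settling at the same time, since the slowest-walk reading would let about two thirds of patients through by chance.

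The reach is limited to the secondary mobility classification and the analyses that use it. The primary 9-HPT rule takes its baseline from assessments 1 to 3 and is not affected. The point is worth correcting, but it does not threaten the trial's main conclusion.

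**What to change.** In 9.4, 10.3.2 and 13.5 (b), replace the definition with wording such as:

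> A mobility responder is a patient whose two on-treatment T25FW walks are both faster than the fastest of the five off-treatment walks (assessments 1, 2, 3, 6 and 9). All other patients are non-responders.

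This corrects the count, gives each sequence one post-fampridine and one post-placebo washout walk in its bar, and removes the word maximum. The two changes belong together: adding Assessment 6 while keeping maximum would loosen the rule on the slowest-walk reading. If there is a reason to leave Assessment 6 out, the plan should state it and explain why it does not apply equally to Assessment 9.

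No new data are needed, because the T25FW is already recorded at Assessment 6. The cost is a stricter rule. In the 2 SD scenarios without trend, responder proportions fall by 4 to 9 points (65 to 61 in both sequences without carryover; 65 to 56 in A and 60 to 56 in B with a 0.5 SD residual). The fall is larger if the residual effect is large: A drops from 47% to 23% when a 1.5 SD effect persists in full. The edit does not remove imbalance from practice or disease trend, so responder proportions should still be shown by sequence.
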